2.2. Study Design

The study design is summarized in the diagram below.

Figure 1. Study Design

This is a randomized, double-blind, placebo-controlled, multicenter, parallel-group, Phase 3 study of the efficacy and safety of tanezumab when administered by SC injection for 16 weeks compared to placebo in subjects with osteoarthritis of the knee or hip. Approximately 690 subjects (approximately 230 per treatment group) will be randomized to one of 3 treatment groups in a 1:1:1 ratio. Subjects will receive a total of two SC injections, separated by 8 weeks:

- *tanezumab 2.5 mg (Day 1) and tanezumab 2.5 mg (Week 8);*
- *tanezumab 2.5 mg (Day 1), and tanezumab 5 mg (Week 8);*
- *placebo to match tanezumab (Day 1) and placebo to match tanezumab (Week 8).*

The randomization will be stratified by the factors of index joint and highest Kellgren-Lawrence grade in the knee and hip joints.

This study is designed with a total (post-randomization) duration of 40 weeks and will consist of three periods: Screening (up to a maximum of 37 days), Double-blind Treatment (16 weeks, 6 in-clinic visits), and Safety Follow-up (24 weeks). The Screening Period (to begin up to 37 days prior to Randomization) includes a Washout Period (lasting a minimum of 2 days for all prohibited pain medications) if required, and an Initial Pain Assessment Period (IPAP; 7 days prior to Randomization/Baseline; minimum 3 days).

The end of treatment period is at Week 16, with the safety follow-up period up to Week 40. The primary time point for efficacy is Week 16. The period of interest for most safety results is the treatment period. Selected safety results will also be provided separately for the safety follow-up period, and some results will be provided for the combined overall study period comprising the treatment and safety follow-up periods.

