The rescue medication data will be converted to Weekly scores for the week prior to the timepoint of interest. Calculation of the endpoints is described in Appendix 3.

The ... number of days of use of rescue medication ... will be analyzed for Weeks 2, 4, 8, 12, and 16... and the amount of rescue medication use per week will be analyzed for Weeks 2, 4, 8, 12, and 16. ... The number of days and amount of rescue medication (mg dosage of acetaminophen) will be analyzed using the Negative Binomial model, with model terms of Baseline WOMAC Pain subscale score, Baseline diary average pain score, index joint, Kellgren-Lawrence grade, and treatment group. In this model the error term is defined with a negative binomial distribution, and 'log' is used as the link function. Estimated levels of rescue medication use will be shown for each treatment group, and the ratio (with 95% CI) for comparisons versus placebo will be shown. Imputation for missing rescue medication data will use LOCF only. For this analysis, Baseline data will not be carried forward in the case of a post-Baseline observation not being available for use in LOCF.

A table showing number and percentage of subjects will summarize the response for each dimension (item) for the EQ-5D-5L™ at Baseline and Week 8 and Week 16. These summary tables will be shown by treatment group. In addition, for each treatment and for each time point assessed, descriptive statistics (mean, standard deviations, median, number of subjects) will characterize the five-item health status profile on the EQ-5D-5L™ in terms of the health utility score, and the EQ-Visual Analog Scale (EQ-VAS).

The HCRU data at Baseline, Week 24, and Week 40 will be summarized.

Summaries of the change from Baseline to Week 16 in the WPAI:OA impairment scores will be shown by treatment group. This summary will use observed data only (no imputation for missing data). The calculation of these endpoints is described in Appendix 3.

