Number of days of rescue medication use during Weeks 2, 4, 8, 12, and 16	ITT	Negative Binomial Model	BL WOMAC Pain, BL diary average pain, Index Joint (Knee/Hip), Highest KL grade (2, 3 or 4), Treatment Group	LOCF	Secondary Endpoint Analysis
Amount (mg) of rescue medication taken during Weeks 2, 4, 8, 12, and 16	ITT	Negative Binomial Model	BL WOMAC Pain, BL diary average pain, Index Joint (Knee/Hip), Highest KL grade (2, 3 or 4), Treatment Group	LOCF	Secondary Endpoint Analysis
EQ-5D-5L dimensions (Mobility; Self-care; Usual activities; Pain/Discomfort; Anxiety/Depression), EQ-VAS and Overall Health Utility at Baseline and Weeks 8 and 16	ITT	Summary	NA	Observed	Secondary Endpoint Analysis
WPAI endpoints (% work time missed; % impairment while working; % overall work impairment; % activity impairment) at Week 16	ITT	ANCOVA	BL score, BL diary average pain, Index Joint (Knee/Hip), Highest KL grade (2, 3 or 4), Treatment Group (study site as a random effect)	Observed	Secondary Endpoint Analysis
Healthcare Resource Utilization at Baseline, Weeks 24 and 40	ITT	Descriptive Summary	Treatment group	Observed	Secondary Endpoint Analysis
Change from baseline to Weeks 2, 4, 8, 12, 16, 24, and 40 in the NIS score, and Change from Baseline to Worst post-Baseline NIS score	ITT	CMH test	Treatment Group [1]	LOCF (Weeks 2, 4, 8, 12, 16, 24, & 40), Worst post-baseline score	Safety Endpoint Analysis
Survey of Autonomic Symptoms (SAS), number of symptoms and total impact score (by visit and change from Baseline)	ITT	Summary	NA	Observed	Safety Endpoint Analysis

[1] CMH test will be stratified by the levels of the combined stratification parameters (6 levels). If there are <15 subjects in any combined stratification level then the CMH test will be unstratified

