How long ago did you quit your job because of your osteoarthritis?	Years and Months	0-99 Years and 0-99 Months (should be max of 11 months)

Rescue Medication Endpoints

Rescue medication data is collected daily using an electronic system up to Week 16, and weekly after Week 16 and up to Week 40. Daily and weekly collected data will be assigned to a specific study week for summary and reporting. The assignment of daily and weekly data to weeks will use the same principle as described above in Appendix 2.1 for the daily and weekly index joint pain data.

The incidence of rescue medication use will look for any incidence in the week of interest (collected through daily or weekly diary data). The number of days of RM use (using daily and weekly data) and the total amount taken (using daily data up to Week 16 only) over the week will be calculated for the assigned week algorithm described above.

Imputation is described in [Section 5.3](#) above. Imputation occurs for daily data up to Week 16 where the subject is in the trial and up to the end of that particular week.

An example of imputation and calculating the three endpoints using the daily diary data is shown below.

Example of calculating rescue medication data from Daily Diary Data (Subject does not discontinue)

In this example, a subject has a Week 2 visit on study day 14 (slightly earlier than the nominal day 15). Study days 8-14 would represent Week 2 data.

Using the Week 2 interval described above for a subject, i.e. study days [8-14], we have the following rescue medication example data.

The amount taken and number of days of rescue medication use is adjusted for the duration of the Weekly interval.

Study Day (Week)	Number of Doses of RM taken [1]	Number of Doses of RM taken [1] with LOCF imputation
8 (Week 2)	2	2
9 (Week 2)	Missing	2 [2]
10 (Week 2)	0	0
11 (Week 2)	1	1

12 (Week 2)	Missing	1 [2]
13 (Week 2)	2	2
14 (Week 2)	0	0

[1] 500mg tablets of acetaminophen; [2] Using LOCF imputation for missing data

For this subject the following data will be calculated for Week 2:

- Incidence of rescue medication taken in Week 2: Yes. Rescue medication taken on days 8, 9 (imputed), 11, 12 (imputed), 13.
- Number of days of rescue medication use in Week 2: 5. For days 8-14 we have rescue medication taken on days 8, 9 (imputed), 11, 12 (imputed), and 13. The number of days taken for the 7 day period is $5/7*7=5$.

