- Amount (mg) of rescue medication use in Week 2: For days 8-14 we have the number of doses taken of 2, 2 (imputed), 0, 1, 1 (imputed), 2, and 0. The number of doses taken for the 7 day period is $8/7*7=8$, making the amount of acetaminophen dosage of 4000mg.

Example of calculating rescue medication data from Daily Diary Data (Subject discontinues)

In this example, a subject discontinues on study day 62, a few days after a Week 8 visit (which was on study day 60). The Week 5-8 data is calculated as described above (e.g. Week 8 using days [50, 56]). The subject has rescue medication data as shown below.

Study Day (Week)	Number of Doses of RM taken [1]	Number of Doses of RM taken [1] with LOCF imputation
57 (Week 9)	1	1
58 (Week 9)	1	1
59 (Week 9)	Missing	1 [2]
60 (Week 9)	Missing	1 [2]
61 (Week 9)	Missing	1 [2]
62 (Week 9)	Missing	1 [2]
63 (Week 9)	Missing	1 [2]

[1] 500mg tablets of acetaminophen; [2] Using LOCF imputation for missing data

Week 9 is calculated as days 57 to 63. The data up to the end of the last week the subject was in the trial is imputed using LOCF as shown above. Therefore the Week 9 scores are then used to impute the Weekly data for summary and analysis for Weeks 10 to 16.

As above the incidence of rescue medication for Week 9 would be ‘Yes’. The number of days of rescue medication use would be 7, and the average dose would be $7/7*7*500=3500\text{mg}$ for this week.

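### Days of rescue use per week can only run from 0 to 7, but the planned negative binomial model has no upper bound, so its confidence intervals and p-values may be miscalibrated, by an amount and in a direction that depend on the data.

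*SAP*

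**What the plan says.** Section 5.2.2 puts both rescue medication quantities under one model: "The number of days and amount of rescue medication (mg dosage of acetaminophen) will be analyzed using the Negative Binomial model". It continues: "In this model the error term is defined with a negative binomial distribution, and 'log' is used as the link function". The reported effect is a ratio: "the ratio (with 95% CI) for comparisons versus placebo will be shown". The Appendix 1 row "Number of days of rescue medication use during Weeks 2, 4, 8, 12, and 16" repeats the negative binomial choice, with Baseline WOMAC Pain, Baseline diary average pain, index joint, Kellgren-Lawrence grade and treatment group as terms.

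Appendix 3 sets the denominator. Its first worked example reads "The number of days taken for the 7 day period is" and then gives 5/7*7=5. The second example shows the upper limit being reached: "The number of days of rescue medication use would be 7". In that example use was recorded on two days (57 and 58) and the other five days of the week were filled by carrying forward. Section 5.2.2 gives the missing-data rule: "Imputation for missing rescue medication data will use LOCF only".

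The SAP mentions no robust variance, scale parameter, dispersion check or fallback model for this endpoint. It also gives no expected mean, variance, share of zeros or sevens, or power for it.

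**The concern.** A negative binomial variance is mu + k*mu^2, which has no ceiling. A score confined to 0-7 with mean mu cannot have variance above mu*(7 - mu). The dispersion k is estimated by maximum likelihood from the whole shape of the data, zeros included, so the fitted variance need not match the actual variance of a bounded count. The model-based standard error of the log ratio takes over that mismatch.

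At stake are two comparisons with placebo at five time points (2 x 5 = 10 ratios, each with a confidence interval). If the standard error is too large, a real reduction in rescue days can be missed. If it is too small, false positives exceed the nominal 5%. The problem concerns days specifically. It arises even though days are a genuine count, and it is separate from any question about modelling the mg amount.

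**Working it through.** **Inputs from the SAP.** "Approximately 690 subjects (approximately 230 per treatment group) will be randomized to one of 3 treatment groups in a 1:1:1 ratio" (Section 2.2), so 690/3 = 230 per arm. Tests are two-sided (5.1.1) at an unadjusted 5% for secondary endpoints (5.1.2). The count runs 0-7 (Appendix 3). The SAP states no figure for this endpoint that could be reproduced. Its worked examples are arithmetically correct: 5/7 x 7 = 5 days, 8 x 500 = 4000 mg, 7 x 500 = 3500 mg.

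**Assumptions.** The distribution of days is assumed. Because no variance estimator is named, the model-based one is taken as planned.

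**Formulas** (two arms, no covariates, equal means):
- True variance of the log ratio: 2V/(n*mu^2), where V is the actual variance of the count.
- Negative binomial model-based variance: 2(mu + k*mu^2)/(n*mu^2).
- Standard error ratio: r = sqrt[(mu + k*mu^2)/V].
- Actual type I error: about 2*Phi(-1.96*r).

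**Results for assumed 0-7 shapes.** There were 3000 simulations per cell. k is the median fitted value under the null. Alternatives were set to give the robust test roughly 80% power. The robust comparator is a sandwich variance on the same log ratio.

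| Shape | mu | V | k | mu + k*mu^2 | Ceiling mu(7-mu) | r, formula | r, simulated | Type I: NB / robust | Power: NB / robust |
|---|---|---|---|---|---|---|---|---|---|
| 50% at 0, rest even over 1-7 | 2.00 | 6.00 | 2.07 | 10.28 | 10.00 | 1.31 | 1.30 | 1.1% / 5.2% | 68% / 85% |
| 30% at 0, rest even over 1-7 | 2.80 | 6.16 | 0.78 | 8.92 | 11.76 | 1.20 | 1.20 | 1.8% / 4.9% | 70% / 82% |
| Even over 0-7 | 3.50 | 5.25 | 0.21 | 6.07 | 12.25 | 1.08 | 1.08 | 3.5% / 4.9% | 76% / 81% |
| Mostly 1-2, 10% at 0, 8% at 7 | 2.13 | 3.61 | 0.26 | 3.31 | 10.37 | 0.96 | 0.96 | 5.9% / 5.1% | 90% / 89% |
| 80% at 1, 20% at 7 | 2.20 | 5.76 | 0.49 | 4.57 | 10.56 | 0.89 | 0.87 | 8.8% / 5.4% | 94% / 90% |
| Half at 0, half at 7 (extreme) | 3.50 | 12.25 | 2.64 | 35.84 | 12.25 | 1.71 | 1.70 | 0.1% / 4.5% | 30% / 81% |

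In the first row the fitted variance, 2 + 2.07 x 4 = 10.28, exceeds the largest variance that any 0-7 score with mean 2 can have, 2 x 5 = 10. The type I formula agrees with simulation: 2*Phi(-1.96 x 1.30) = 1.1% in the first row and 2*Phi(-1.96 x 0.87) = 8.8% in the fifth.

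**Beta-binomial counts out of 7**, where rho is the within-subject correlation of days:
- rho 0.1-0.2: type I error 3.9-6.2%, power loss 0-3 points.
- rho 0.3: type I error 2.5-5.1%, power loss about 3-5 points.
- rho 0.5-0.6 (many 0s and 7s): type I error 1.1-2.0%, standard error about 20-30% too large, power loss about 13-21 points. A wider grid (rho 0.5-0.7, means 1-4) gives 0.5-2.5% and about 8-25 points.
- rho 0 (every subject has the same daily probability, which is hard to credit): type I error 0.5-3.4%. Here V = mu(1 - mu/7) lies below mu, and the negative binomial variance cannot fall below mu.

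**With covariates** (600 runs per cell), negative binomial type I error was 4.8% at mean 2, rho 0.2 and 2.0% at mean 3, rho 0.6. Power was 82% against 85%, and 58% against 80%. The comparator there was a binomial model out of 7 with robust variance, which itself ran at 6-7% type I error, so part of that power gap is overstated.

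**The case against.** A reader might infer that the planned test is necessarily conservative and loses substantial power. The documents do not support that. They give no distribution for rescue days, and both the size and the sign of the error depend on it. A large share of zeros alone is not enough: at mean 2 and rho 0.2, with 25% zeros and 1% sevens, type I error was 3.5% and the standard error ratio 1.07. Clear conservatism needs either heavy mass at both ends or a broad spread alongside many zeros. Few zeros with a cluster at 7 turns the error round.

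Two further points on the plan's side stand. The bound does not in itself bias the log-link ratio; only its model-based variance is in question. And Section 5.1.2 leaves this endpoint outside the multiplicity strategy, while Section 5.2.1 also analyses any rescue use by logistic regression, so conclusions on rescue do not rest on the days model alone.

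What the objection does not remove is the mismatch itself. The SAP's own imputation also makes the harmful shape more plausible. Daily carry-forward turns two recorded days into 7 of 7 in the Appendix 3 example, and Section 5.3 then carries the weekly score forward after discontinuation, to Week 16. That raises the plausibility of heavy 0s and 7s but does not establish it.

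**Conclusion.** The point holds in conditional form. An unbounded variance model is specified for a count that cannot exceed 7, with no safeguard, so the intervals and p-values for number of days are not assured of their nominal properties. The effect runs from negligible at moderate spread, through clear conservatism when many subjects sit at 0 and 7, to mild or moderate anti-conservatism with few zeros and a cluster at 7. All of these sizes rest on assumed distributions, 230 per arm and, for the main ranges, a model without covariates. The half-0, half-7 case is a limit, not an expectation. The consequence is confined to an unadjusted secondary endpoint; the co-primary and key secondary tests are untouched. The change is worth making because one remedy covers both directions, not because a particular loss has been shown.

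**What to change.** For number of days only, keep the log link, the covariates and the ratio versus placebo, and state in Section 5.2.2 and in the matching Appendix 1 row that standard errors, confidence intervals and p-values use an empirical (sandwich) variance. The mean model may be Poisson or negative binomial; name one in advance. In the simulations without covariates the robust variance held type I error at about 4-6% in every shape tested.

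A binomial model out of 7 is not the preferred route. Its usual logit link would replace the planned ratio with an odds ratio.

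The cost is one sentence and one model option, with no new data. The downside is slightly wider confidence intervals where the model-based standard error would have been too small. The change should be made before unblinding.

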5.1.2. Statistical Decision Rules

The Type I error rate (α -level) used in the assessment of pair-wise treatment comparisons for the primary efficacy endpoints is 5%. The fixed sequence testing strategy of the co-primary endpoints is described below.

The assessment of significance for the tanezumab versus placebo treatment contrasts will use a step-down testing strategy within each of the co-primary efficacy endpoints. The step-down testing will first test tanezumab 2.5/5 mg versus placebo, and if statistically significant ($p \leq 0.05$) will then test tanezumab 2.5 mg versus placebo. Finally, the particular tanezumab dose group is declared as superior to placebo if the corresponding treatment contrast is significant over all three co-primary endpoints. This testing procedure will maintain the Type I error to 5% or less within each of the co-primary efficacy endpoints, and to less than 5% for all three co-primary efficacy endpoints.

The secondary endpoint of subjects with $\geq 50\%$ reduction from baseline in WOMAC Pain at Week 16 is identified as a key secondary endpoint and will be included in the testing strategy. If both tanezumab regimens are found to be statistically significantly better than placebo in the primary comparisons described above, the two comparisons of this secondary endpoint (tanezumab 2.5 mg treatment group versus placebo and tanezumab 2.5/5 mg treatment group versus placebo) will be adjusted for multiple comparisons using the Hochberg procedure and an overall significance level of 0.05.

The primary analysis will be that with the multiple imputation approach (see below for details), and thus the overall type I error is controlled for each of the two dose regimens (2.5 mg and 2.5/5 mg) since all three co-primary endpoints need to be significant for a single dose. The overall type I error of the study is also controlled given the step-down testing strategy for each of the primary endpoints and the key secondary endpoint. Control of the type I error rate accounting for multiplicity of contrasts will only apply to the three co-primary endpoints (model with the primary imputation analysis) and the key secondary endpoint.

Regardless of the outcome of the primary and key secondary analyses, the secondary endpoints will be tested. No adjustment for multiple comparisons will be made for the secondary efficacy, and for the safety endpoints. The α -level for each hypothesis test for the secondary and exploratory analyses will be 5%.

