The incidence ... of use of rescue medication... will be analyzed for Weeks 2, 4, 8, 12, and 16... The incidence of use of rescue medication will be analyzed using logistic regression for binary data, with model terms for Baseline WOMAC Pain subscale score, Baseline diary average pain, index joint, Kellgren-Lawrence grade, and treatment group. ... Estimated levels of rescue medication use will be shown for each treatment group, and the ratio (with

95% CI) for comparisons versus placebo will be shown. Imputation for missing rescue medication data will use LOCF only.

The incidence of treatment withdrawal due to lack of efficacy ('Insufficient Clinical Response' on the Subject Summary Case Report form) will also be analyzed for discontinuation up to Week 16 (end of treatment period). The analysis of the incidence of discontinuation due to lack of efficacy will be made using logistic regression for binary data, with model terms for Baseline WOMAC Pain subscale score, Baseline diary average pain score, index joint, Kellgren-Lawrence grade, and treatment group. Discontinuation in the post-treatment safety follow-up period will not be included in this endpoint for analysis, but will be summarized as part of the safety tables.

Cumulative WOMAC Pain response and WOMAC Physical Function at Week 16 using response definitions from a reduction of >0% to =100% (in steps of 10%) will be summarized, using mixed BOCF/LOCF (as described above), and also LOCF and BOCF imputation for WOMAC Pain and WOMAC physical function. Imputation with BOCF for subjects with missing data at that timepoint will lead to the subjects being assessed as non-responders for the response endpoint.

The proportion of subjects who meet a WOMAC Pain response definition at Week 16 will be examined in the cohort of subjects who had a WOMAC Pain response to treatment at Week 8 and the cohort of subjects who did not have a WOMAC Pain response at Week 8. Treatment comparisons will be made within each cohort for tanezumab 2.5/5 mg versus placebo and tanezumab 2.5 mg versus placebo. A descriptive comparison will also be made between the treatment groups of tanezumab 2.5/5 mg versus tanezumab 2.5 mg. These analyses will be produced for the WOMAC Pain response levels of 30% and 50%, and other response definitions (15%). This is an exploratory analysis as treatment comparisons are not specifically powered to achieve significance within cohorts of subjects.

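### The weekly rescue amount is modelled as negative binomial in mg although the data are 500 mg tablet counts, so under the usual fit its CI and p-value depend on the unit

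*SAP*

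**What the plan says.** SAP Section 5.2.2 states that the "amount of rescue medication (mg dosage of acetaminophen) will be analyzed using the Negative Binomial model". The only further detail on the model is "In this model the error term is defined with a negative binomial distribution", a log link, and the covariates: baseline WOMAC Pain, baseline diary pain, index joint, Kellgren-Lawrence grade and treatment. The result shown is a ratio to placebo with a 95% CI. Appendix 1 repeats the unit: "Amount (mg) of rescue medication taken during Weeks 2, 4, 8, 12, and 16".

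Appendix 3 (Rescue Medication Endpoints) shows what is recorded. The daily entry is a number of doses, footnoted as "1] 500mg tablets of acetaminophen". The week's doses are summed and multiplied by 500; the first worked example ends with 8 doses, "making the amount of acetaminophen dosage of 4000mg". The appendix also says: "The amount taken and number of days of rescue medication use is adjusted for the duration of the Weekly interval".

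No dispersion estimator, scale parameter or variance estimator is named for this model.

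**The concern.** A negative binomial model ties the variance to the mean as mu + alpha·mu². If tablets Y follow it, then 500Y, with mean mu' = 500·mu, has variance 500·mu' + alpha·mu'². That is not a negative binomial variance, because the family is not closed under a change of unit. A maximum-likelihood fit in mg therefore has to describe values that are zero or multiples of 500 as if they were counts of single milligrams. It re-estimates alpha, and the model-based standard error moves with it.

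At stake are the CI and p-value of the amount ratio at Weeks 2, 4, 8, 12 and 16. They would partly reflect the choice of mg over tablets, which carries no information about treatment.

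**Working it through.** **1. The SAP's own figures.** Appendix 3, first example: 2+2+0+1+1+2+0 = 8 doses; 8/7×7×500 = 4000 mg. Second example: 7/7×7×500 = 3500 mg. Both reproduce. The mg value is the tablet count times 500.

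**2. Inputs.** About 230 per arm in three arms (Section 2.2), two-sided tests (Section 5.1.1) and 5% for secondary endpoints (Section 5.1.2). The SAP gives no mean weekly use, dispersion, share of zero-use weeks or expected ratio. All such values below are assumptions.

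**3. One case by hand.** Assume tablets are negative binomial with placebo mean 6, alpha 2 and ratio 0.65 (active mean 3.9). With treatment only, SE² of the log ratio = Σ over the two arms of (1/mu + alpha)/n.
- Tablets: [(1/6 + 2) + (1/3.9 + 2)]/230 = 4.4231/230, so SE = 0.139.
- mg (means 3000 and 1950): matching the true variance needs alpha = 2 + 1/6 − 1/3000 = 2.17 for placebo and 2 + 1/3.9 − 1/1950 = 2.26 for active. Maximum likelihood instead gives about 6.0, because the zeros must be explained. The zero probability is (1 + alpha·mu)^(−1/alpha). In tablets it is 13^(−1/2) = 28% for placebo. In mg with alpha 2 it would be 6001^(−1/2) = 1.3%, and alpha 6 raises it to 18001^(−1/6) = 20%.
- With alpha 6: [(1/3000 + 6) + (1/1950 + 6)]/230 = 12.0008/230, so SE = 0.228.
- Power: ln 0.65 = −0.431. In tablets, Φ(0.431/0.139 − 1.96) = 87%. In mg the estimate still varies with SD 0.139 but must exceed 1.96×0.228 = 0.448, so Φ((0.431 − 0.448)/0.139) = 45%.
- Simulation of this case gave SE 0.138 against 0.228 and power 87% against 47%. With no effect, rejection was 5.3% in tablets and 0% in mg.

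**4. One fixed simulated dataset** (2×230, 32% zeros). Tablets: ratio 0.788, CI 0.60 to 1.04, p = 0.091. mg: ratio 0.788, CI 0.50 to 1.23, p = 0.298.

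**5. Range if tablets are negative binomial.** Means 2 to 15 by alpha 0.3 to 4, 25 cells, ratio of mg SE to tablet SE:

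| Zero-use weeks | Cells | mg SE / tablet SE |
|---|---|---|
| 0.4–1.4% | 3 | 1.07–1.14 |
| 3–11% | 7 | 1.22–1.58 |
| 14–20% | 3 | 1.37–1.64 |
| 21–36% | 7 | 1.43–1.96 |
| 40–58% | 5 | 1.50–1.89 |

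A single dataset with no zeros gave 0.0554/0.0538 = 1.03. With a moment-based dispersion the ratio was 0.999 to 1.001 in all 25 cells.

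**6. Other count shapes** (SE in tablets, then mg):
- 40% structural zeros plus negative binomial (mean 10, alpha 0.5): 0.162, 0.277; robust 0.120. Null rejection was 0% in both units.
- Binomial(14, 0.4), 0.1% zeros: 0.0394, 0.0335.
- Binomial(7, 0.5), 0.8% zeros: 0.0499, 0.0448.
- 95% Poisson(6) with 5% Poisson(50), 0.2% zeros: 0.0723, 0.0701. Null rejection was 20.0% and 21.5%.
- Poisson-lognormal with an assumed cap of 56 tablets a week (the SAP states no cap), null rejection tablets / mg / robust: 8.8/0.8/5.8%, 8.2/2.3/4.8% and 6.2/0.9/5.9%.

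**7. Robust variance.** With treatment only, SE² = Σ s²/(n·mean²). Multiplying by 500 scales s² and mean² alike, so it cancels exactly. With the SAP's covariates the two units agreed to about 0.001 (for example 0.104 and 0.105). Null rejection with it stayed at about 4 to 7% in a further set of null scenarios, where the model-based fits ranged from 0% to above 20%.

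**The case against.** The strongest reply is that the SAP leaves the estimator open. A moment-based dispersion or a robust variance would make the unit irrelevant, so the text does not state a wrong result. That is true, and the finding is conditional on the usual fit for this reason. But the text as written permits, and would commonly lead to, a fit whose interval changes with the unit, and nothing in it prevents this.

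Three stronger readings are tempting and not supported:
- *The mg interval is always too wide once zero weeks occur.* It was wider for negative binomial, zero-inflated and capped Poisson-lognormal counts. It was narrower for the two binomial shapes and the 95/5 Poisson mixture, all with under 1% zeros.
- *The tablet fit is the correct reference.* That holds only if tablets really are negative binomial, and the power figures assume it. With zero-inflated counts the tablet fit was itself far too conservative; with capped Poisson-lognormal counts it over-rejected.
- *The error rate is exceeded in either unit because use is heavy-tailed.* Unbounded heavy-tailed use can produce this, but no figure in the SAP supports such data, so nothing here rests on it.

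It is also fair to say that little depends on this endpoint. Section 5.1.2 says "No adjustment for multiple comparisons will be made for the secondary efficacy" endpoints, and the same construct is covered by number of days and by incidence, for which "The incidence of use of rescue medication will be analyzed using logistic regression for binary data".

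**Conclusion.** The point holds as a minor one. Under maximum-likelihood dispersion with model-based standard errors, which the SAP neither requires nor excludes, the CI and p-value of the amount ratio depend on whether the data are entered as tablets or mg; the ratio itself does not. If tablets are negative binomial, the mg standard error is roughly 1.1 to 2 times the tablet one. For other shapes the gap can be small or slightly reversed. Since the SAP gives nothing about the distribution of use, neither the size nor the direction can be fixed in advance.

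Only the weekly amount is affected. Number of days is already a count and incidence is a logistic model. The co-primary endpoints and the key secondary endpoint do not use this model, and no trial decision rests on it.

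**What to change.** State in Section 5.2.2 that the 95% CI and p-value for the ratio of rescue amounts use a robust (sandwich) variance. This removes the unit dependence and does not rely on the negative binomial variance being right. Amend the Appendix 1 row to match.

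Optionally, also fit the weekly number of 500 mg tablets, with the same terms and the same LOCF rule, and multiply fitted means by 500 for display in mg. Any non-integer tablet values from the weekly-interval adjustment are no obstacle, because the estimating equations do not need integers. Changing the unit alone is not enough, since the tablet fit can also be miscalibrated.

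The cost is a line of wording and minor recoding. A robust variance may still over-reject slightly if use is very heavy-tailed.
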